8.2.3 Specimen Preparation, Handling, and Shipping

As a central laboratory will be used for specimen analysis, the PI and all members of the investigational team will be instructed to follow the instructions of the central laboratory manual provided by the central laboratory concerning specimen preparation, handling, storage, and shipment.

Compound No.: GTx-024 Author: [name]

9 ASSESSMENT OF SAFETY

9.1 Methods and Timing for Assessing, Recording, and Analyzing Safety Parameters

9.1.1 Adverse Events

ICH E6 guidelines define an AE as any untoward medical occurrence in a subject or clinical investigation subject administered a pharmaceutical product regardless of its causal relationship to the study treatment. An AE can therefore be any unfavorable and unintended sign (including an abnormal laboratory finding), symptom, or disease temporally associated with the use of medicinal (investigational) product, whether or not considered related to the medicinal (investigational) product.

The occurrence of an AE may come to the attention of study personnel during study visits and interviews of a study subject presenting for medical care, or upon review by a study monitor.

The period of observation for which AEs are to be collected begins after the subject has signed the ICF, throughout the study intervention period, and for 28 days post treatment.

All AEs, whether reported by the subject or noted by study personnel, will be recorded in the subject's medical record and captured on the appropriate eCRF.

Information to be collected includes event description, time of onset, Investigator's assessment of severity, Investigator's assessment of relationship to study drug, and time of resolution/stabilization of the event. All AEs occurring while on study must be documented appropriately regardless of relationship to study drug. All AEs will be followed to adequate resolution as per Section 9.3 Type and Duration of Follow-up of Subjects after Adverse Events.

Compound No.: GTx-024 Author: [name]

Any medical condition that is present at the time that the subject is screened will be considered as baseline and not reported as an AE. However, if the condition deteriorates at any time during the study, it will be recorded as an AE.

All AEs must be graded for intensity and relationship to study drug.

9.1.2 Intensity of Event:

All AEs will be assessed by the Investigator according to NCI-CTCAE 4.0. For any AE that is not specifically covered in NCI-CTCAE 4.0, the criteria from Table 2 should be used:

Table 2: Description of Grades According to the NCI-CTCAE	
Grade	Description
0	No AE or within normal limits
1	Mild; asymptomatic or mild symptoms; clinical or diagnostic observations only; intervention not indicated
2	Moderate; minimal, local, or non-invasive intervention indicated; limiting age-appropriate instrumental activities of daily living
3	Severe or medically significant but not immediately life-threatening; hospitalization or prolongation of hospitalization indicated; disabling; limiting self-care activities of daily living
4	Life-threatening consequences; urgent intervention indicated
5	Death related to AE

Compound No.: GTx-024
Author: [name]

If the intensity changes within a day, the maximum intensity should be recorded. If the intensity changes over a longer period of time, the changes should be recorded as separate events (having separate onset and stop dates for each change in intensity).

Changes in the intensity of an AE will be documented to allow an assessment of the duration of the event at each level of intensity to be performed. AEs characterized as intermittent require documentation of onset and duration of each episode.

9.1.3 Drug-Adverse Event Relationship

The causal relationship of the study drug to the AE will be assessed by the Investigator.

If there is a reasonable suspected causal relationship to the study treatment, i.e., there are facts (evidence) or arguments to suggest a causal relationship, the drug-event relationship should be assessed as related.

The following criteria should be considered by the Investigator to assess the relationship (or association) of each AE to the study drug:

- **Related** There is a reasonable causal relationship to the study treatment, i.e., there is evidence or arguments to suggest a causal relationship. The following criteria should be considered in order to assess the relationship as related:
 - Reasonable temporal association with drug administration
 - It may or may not have been produced by the subject's clinical state, environmental or toxic factors, or other modes of therapy administered to the subject
 - Known response pattern to suspected drug
 - Disappears or decreases on cessation or reduction in dose
 - Reappears on rechallenge
- Not related This category applies to any AE that does not appear to have a reasonable relationship to the use of study drug (see above guidelines)

Compound No.: GTx-024 Author: [name]

9.1.4 Serious Adverse Events

An SAE is defined as an AE that meets one of the following conditions:

- Death
- Life-threatening event (defined as a subject at immediate risk of death at the time of the event)
- An event requiring inpatient hospitalization or prolongation of existing hospitalization
- Results in congenital anomaly or birth defect
- Results in a persistent or significant disability/incapacity
- Any other important medical event that may not result in death, be life threatening, or require hospitalization, may be considered a serious adverse experience when, based upon appropriate medical judgment, the event may jeopardize the subject and may require medical or surgical intervention to prevent one of the outcomes listed above. Examples of such medical events include allergic bronchospasm requiring intensive treatment in an emergency room or at home, blood dyscrasias or convulsions that do not result in inpatient hospitalization, or the development of drug dependency or drug abuse

All SAEs will be:

- Recorded on the appropriate eCRF
- Reported to the designated Safety department/pharmacovigilance contractor using a SAE Report Form within 24 hours of awareness
- Followed through resolution by a study Investigator
- Reviewed and evaluated by a study Investigator

Compound No.: GTx-024 Author: [name]

9.1.5 Procedures to be Followed in the Event of Abnormal Laboratory Test Values or Abnormal Clinical Findings

Clinical laboratory values will be listed with abnormal values flagged. Clinically significant laboratory values will be reported as an AE. The AE will be followed to resolution as per Section 9.3 Type and Duration of Follow-up of Subjects after Adverse Events.

9.2 Reporting Procedures

9.2.1 Serious Adverse Events

All SAEs, including death due to any cause, which occur after the subject signs the ICF and within 28 days following the last administration of study drug, whether or not related to the study drug, must be reported immediately to the designated Safety Department/pharmacovigilance contractor within **24 hours** by e-fax, e-mail, or telephone (see contact information below). At the very least, the following information must be reported:

- Date and time of report
- Reporter's name and phone number
- Investigator's name and site number
- Subject number
- SAE information: event term, onset date, causal relationship
- Study drug: start date of study drug and whether or not study drug has been withheld or discontinued

SAE Reporting Contact Information:

UK Safety E-Fax Line: [name]

UK Safety Unmanned [contact]**US Safety Toll-Free E-Fax Line: **[name]**

Compound No.: GTx-024 Author: [name]

US Safety Toll-Free Unmanned [contact]

Cmed Safety E-mail: [contact]

Information about all SAEs is collected and recorded on the SAE Report Form. The Investigator must assess the relationship of any SAE to study drug, complete the SAE Report Form in English, and send the completed, signed form by e-fax or e-mail within 24 hours to the assigned drug safety group. As a back-up, the site may report SAEs using the unmanned safety hotline, with a completed SAE Report Form forwarded to the assigned drug safety group within 24 hours following notification on the hotline. The original copy of the SAE Report Form and the e-fax confirmation sheet must be kept with the case report form documentation at the study site.

Follow-up information must also be sent to the same assigned drug safety group by e-fax or e-mail using a either new SAE Report Form stating that this is a follow-up to the previously reported SAE (giving the date of the original report), or by using a follow-up query form.

If an SAE is not previously documented (new occurrence) in the Investigator's Brochure (IB) and is thought to be related to the relevant Investigational Medicinal Product (IMP), the assigned drug safety group may urgently require further information from the Investigator for regulatory authority reporting. The drug safety group may need to issue an Investigator Notification (IN) to inform all Investigators involved in any study with the same drug that this SAE has been reported. Suspected Unexpected Serious Adverse Reactions (SUSARs) will be collected and reported to the regulatory/competent authorities and relevant IRBs/IECs in accordance with Food and Drug Administration (FDA) regulations 21 Code of Federal Regulations (CFR) 312.32, ICH guidelines, and European Clinical Trials Directive 2001/20/EC, or as per national regulatory requirements in participating countries. Adequate documentation must be maintained showing that regulatory authorities and IRBs/IECs have been properly notified.

SAEs must be reported within 24 hours, regardless of relationship, on a SAE Report Form to allow the Sponsor to take appropriate measures to address potential new risks in a clinical trial. The Investigator must report such events to the Sponsor

Compound No.: GTx-024 Author: [name]

immediately; under no circumstances should reporting take place more than 24 hours after the Investigator learns of the event.

The term sudden death should be used only when the cause is of a cardiac origin as per standard definition. The terms death and sudden death are clearly distinct and must not be used interchangeably. The study will comply with all local regulatory requirements and adhere to the full requirements of the ICH Guideline for Clinical Safety Data Management, Definitions and Standards for Expedited Reporting, Topic E2.

The SAE Report Form must be signed by the PI or assigned designee.

Other supporting documentation of the event may be requested by the Safety Department/pharmacovigilance contractor and should be provided as soon as possible.

All SAEs will be followed until satisfactory resolution as per Section 9.3 Type and Duration of Follow-up of Subjects after Adverse Events.

9.2.2 Regulatory Reporting

Suspected (considered related to the study drug) and unexpected (not previously described in the reference safety document) serious adverse reactions (SUSARs) will be reported in an expedited manner by GTx, Inc. to regulatory authorities, EudraVigilance, IECs, IRBs and Investigators in compliance with FDA regulations 21 CFR 312.32, ICH guidelines, the European Clinical Trials Directive 2001/20/EC, the European Commission's "Detailed guidance on the collection, verification, and presentation of adverse event/reaction reports arising from clinical trials on medicinal products for human use" (CT-3, June 2011) and other applicable local regulations and guidelines. The timelines stipulated by applicable national regulations and guidelines shall be adhered to, typically death and life-threatening SUSARs shall be reported within 7 days and all other SUSARs shall be reported within 15 days.

Additionally, events may occur during a clinical trial which do not fall within the definition of a SUSAR and thus are not subject to the reporting requirements for GTx ER+/AR+ Protocol; Version 1.0 26May2015 CONFIDENTIAL Page **84** of **121**

Compound No.: GTx-024 Author: [name]

SUSARs, even though they may be relevant in terms of subject safety. Examples are new events related to the conduct of a trial or the development of an IMP likely to affect the safety of subjects such as:

- An SAE which could be associated with the trial procedures and which could modify the conduct of the trial
- A significant hazard to the subject population such as lack of efficacy of an IMP used for the treatment of a life-threatening disease
- A major safety finding from a newly completed animal study (such as carcinogenicity)
- A temporary halt of a trial for safety reasons if the trial is conducted with the same IMP in another country by the same Sponsor, recommendations of the SMC, if any, where relevant for the safety of subjects

These events/observations are not to be reported as SUSARs, but they might require other action, such as urgent safety measures and their notification, substantial amendments, or early termination of the trial, and shall be reported in accordance with applicable local regulations and guidelines.

All serious events designated as expected and/or "not related" to study drug(s), will be reported to the applicable regulatory authorities and IECs/IRBs at least annually in a summary format.

9.2.3 Other Adverse Events

Progression of Underlying Malignancy

If progression of underlying malignancy is clearly consistent with the suspected progression of the underlying cancer as defined by RECIST 1.1, or other criteria as determined by the protocol, it should not be reported as an AE. Similarly, hospitalization due exclusively to the progression of underlying malignancy should NOT be reported as an SAE. Clinical symptoms of progression may be reported as AEs if the symptom cannot be determined as solely due to the progression of the

Compound No.: GTx-024 Author: [name]

underlying malignancy, or does not meet the expected pattern of progression for the disease under study.

If there is any uncertainty about an AE being due only to the disease under study, it should be reported as an AE or SAE.

Liver Toxicity Management

Elevated ALT or AST (> 3 × ULN) in combination with either an elevated total bilirubin (> 2 × ULN) or clinical jaundice in the absence of cholestasis or other causes of hyperbilirubinemia is considered to be an indicator of severe liver injury. Therefore, Investigators must report the occurrence of either of the following as an SAE:

- Treatment-emergent ALT or AST > 3 × ULN in combination with total bilirubin
 2 × ULN (of which 35% is direct bilirubin)
- Treatment-emergent ALT or AST > 3 × ULN in combination with clinical jaundice

For subjects with liver metastasis and elevated ALT or AST of > $3 \times ULN$ at baseline, the values will not be reported as an SAE if $\leq 5 \times ULN$.

The most appropriate diagnosis or (if a diagnosis cannot be established) the abnormal laboratory values should be recorded on the eCRF and reported to the Sponsor within 24 hours after learning of the event, as per Section 9.2

Reporting Procedures.

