- 7. Subject must have either measurable disease or bone-only non-measurable disease, evaluable according to RECIST 1.1
- 8. Adequate organ function as shown by:
 - Absolute neutrophil count (ANC) ≥ 1,500 cells/mm³
 - Platelet count ≥ 100,000 cells/mm³
 - Hemoglobin (Hgb) ≥ 9.0 g/dL
 - Serum aspartate aminotransferase (AST) and alanine transaminase (ALT) ≤ 2.5 upper limit of the normal range (ULN) (or ≤ 5 if hepatic metastases are present)
 - Total serum bilirubin ≤ 2.0 × ULN (unless the subject has documented Gilbert Syndrome)
 - Alkaline phosphatase levels ≤ 2.5 × ULN (≤ 5 × ULN in subjects with liver metastasis)
 - Serum creatinine ≤ 2.0 mg/dL or 177 µmol/L
 - International normalized ratio (INR) or activated partial thromboplastin (aPTT)
 1.5 × ULN (unless on anticoagulant treatment at screening)
- Subject has an Eastern Cooperative Oncology Group (ECOG) performance status⁴
 o or 1
- 10. Subject is able to swallow capsules
- 11. Able and willing to give voluntary, written and signed informed consent before any screening procedure and according to local guidelines

Compound No.: GTx-024 Author: [name]

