9.4 Halting Rules

If in the opinion of the Investigator, the participation in the study is or is becoming detrimental to the well-being of a particular subject, this issue should be discussed with the Medical Monitor for this study and a determination made regarding dose reduction, interruption, or withdrawal of the subject from the study.

Dose reduction, interruption, or withdrawal of the subject from the study should be considered if:

- ALT or AST > 8 × ULN
- ALT or AST > 5 × ULN for more than 2 weeks
- ALT or AST > 3 × ULN and (total bilirubin > 2 × ULN or INR > 1.5)

Compound No.: GTx-024 Author: [name]

 ALT or AST > 3 × ULN with the appearance of fatigue, nausea, vomiting, right upper quadrant pain or tenderness, fever, rash, and/or eosinophilia (> 5%)

For subjects with known liver metastasis and elevated ALT or AST of ≤ 5 × ULN at baseline, discontinuation of treatment should be considered if:

ALT or AST > 5 × ULN and total bilirubin > 2 × ULN

All subjects discontinued from dosing should be followed until abnormal values return to normal.

ALL DISCONTINUATIONS SHOULD BE DISCUSSED WITH THE MEDICAL MONITOR PRIOR TO DISCONTINUATION.

If any 2 out of the first 10 subjects enrolled in the 18 mg arm meet the above hepatotoxicity criteria, or if a total of 5 subjects ever meet these criteria in the 18 mg arm, the 18 mg dose will be reduced to 9 mg for all subjects; the 18 mg arm will be permanently halted and all subjects will be enrolled into the 9 mg arm.

If a total of 5 subjects in the 9 mg arm ever meet the above hepatotoxicity criteria, the study will be halted.

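### The liver-metastasis exemption in Section 9.2.3 tests ALT/AST only, so it either does nothing or removes the automatic SAE trigger from a combined enzyme-bilirubin or enzyme-jaundice event

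*Combined protocol and SAP*

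**What the plan says.** **Triggers (Section 9.2.3, Liver Toxicity Management).** Two combinations must be reported as SAEs. One begins "Treatment-emergent ALT or AST > 3 × ULN in combination with total bilirubin" and continues with a limit of 2 × ULN and a direct-bilirubin condition. The other is "Treatment-emergent ALT or AST > 3 × ULN in combination with clinical jaundice". The lead-in says that the combination, when cholestasis and other explanations for the bilirubin are absent, "is considered to be an indicator of severe liver injury".

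**Exemption (same section).** For subjects with liver metastasis and ALT/AST above 3 × ULN "at baseline, the values will not be reported as an SAE if" they are no higher than 5 × ULN. No condition on bilirubin or jaundice is attached.

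**Eligibility (Section 5.1, criterion 8).** The ALT/AST limit is relaxed ("or ≤ 5 if hepatic metastases are present"), so subjects between 3 and 5 × ULN can enrol. Bilirubin is not relaxed for liver metastasis: "Total serum bilirubin ≤ 2.0 × ULN (unless the subject has documented Gilbert Syndrome").

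**Halting (Section 9.4).** The general list includes "ALT or AST > 3 × ULN and (total bilirubin > 2 × ULN or INR > 1.5"). A separate line for known liver metastasis with baseline ALT/AST up to 5 × ULN reads "ALT or AST > 5 × ULN and total bilirubin > 2 × ULN". Subjects who meet the hepatotoxicity criteria above are then counted: 2 of the first 10, or 5 in total, closes the 18 mg arm, and 5 in the 9 mg arm halts the study.

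**The concern.** The exemption appears meant to stop stable, metastasis-related enzyme values from generating SAEs. The rule it modifies does not report enzyme values on their own, so that purpose is already met. What the sentence can still act on is the combined event, and it does so without looking at the part of the event that has changed.

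Section 2.3.1 reports dose-dependent ALT increases with this drug but no significant bilirubin increases in subjects with elevated ALT. A combined event would therefore be a new finding. Section 2.2 describes longer dosing at 1, 3 and 9 mg for up to 184 days, and doses up to 30 mg for up to 14 days; the 18 mg arm may run for 24 months. At stake is whether such an event, in a subject with liver metastasis, reaches the 24-hour SAE process automatically or only through someone's judgement.

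**Working it through.** There is no sample size, power or alpha to reproduce here. The check is of the reporting logic.

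**Step 1. Write out the rules.**
- Trigger: ALT/AST > 3 × ULN AND (bilirubin > 2 × ULN OR jaundice).
- Exemption: liver metastasis AND baseline ALT/AST > 3 × ULN AND current ALT/AST ≤ 5 × ULN.
- Cancelled report: trigger AND exemption.

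Because the trigger requires bilirubin > 2 × ULN or jaundice, every cancelled report contains one of them. No cancelled report is an isolated enzyme rise.

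**Step 2. Test the undefined term.** Treatment-emergent is not defined in the documents, so three readings were tried on a grid for subjects with liver metastasis: baseline ALT/AST 2, 3.5, 4, 5; on-treatment ALT/AST 2.5, 3.2, 4, 4.8, 5, 5.5, 8.5; bilirubin 1, 2, 2.5, 6 (all × ULN); jaundice no or yes. That is 4 × 7 × 4 × 2 = 224 combinations. Of the 8 bilirubin-jaundice pairs, 6 satisfy the second limb of the trigger.

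| Reading of treatment-emergent | Triggered | Cancelled by the exemption | Cancelled with bilirubin ≤ 2 × ULN and no jaundice |
|---|---|---|---|
| Any on-treatment value > 3 × ULN | 4 × 6 × 6 = 144 | 3 × 4 × 6 = 72 | 0 |
| > 3 × ULN and new or above baseline | (6 + 5 + 4 + 2) × 6 = 102 | (3 + 2 + 0) × 6 = 30 | 0 |
| New crossing of 3 × ULN only | 1 × 6 × 6 = 36 | 0 | 0 |

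The counts depend on the grid chosen. The zeros follow from the rules.

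**Step 3. Is the bilirubin rise new?** Entry bilirubin is at most 2.0 × ULN except in Gilbert Syndrome. Outside that exception, an on-treatment value above 2 × ULN has arisen since entry. No such guarantee exists for Gilbert subjects, and the jaundice trigger has no direct-bilirubin condition.

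**Step 4. Set 9.2.3 beside 9.4.** Take baseline ALT 3.2 × ULN with normal bilirubin, then ALT 4.9 and bilirubin 6 × ULN, with the exemption read as cancelling the trigger.

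| If the liver-metastasis line in 9.4 | Liver SAE trigger in 9.2.3 | Counts toward halting under these two criteria |
|---|---|---|
| adds to the general list | cancelled | yes (4.9 > 3 and 6 > 2) |
| replaces the general list | cancelled | no (4.9 is not > 5) |

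Section 9.4 does not say which applies. In the first case an event counts toward halting without meeting the liver SAE trigger; in the second it reaches neither.

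**Step 5. How many subjects?** The documents give no prevalence. Assume that 20–40% of up to 118 randomised subjects have liver metastases, and that 5–10% of those enter with ALT/AST between 3 and 5 × ULN:
- low: 118 × 0.20 × 0.05 = 1.2
- high: 118 × 0.40 × 0.10 = 4.7

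These are exempt subjects, not events. If a further 5–10% of them had a combined event, the expected number would be 1.18 × 0.05 = 0.06 to 4.72 × 0.10 = 0.47.

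**The case against.** **The sentence may be harmless.** If treatment-emergent means a new crossing of 3 × ULN, these subjects never meet the trigger and nothing is cancelled. If the values means only the enzymes just named, bilirubin and jaundice are untouched; jaundice is a clinical sign and not obviously a value at all. Both readings are available. Neither gives the sentence a use, and a site reading the literal instruction not to report may take it the other way. The 5 × ULN limit also suggests that its author expected the trigger to apply to these subjects above that level, which the strict reading would not allow.

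**The exemption may be deliberate.** Together with the liver-metastasis line in 9.4, it could be a planned move of the enzyme limb from 3 to 5 × ULN. That is possible, but the text does not say so.

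**Other routes remain.** A reader might infer that these events are barred from SAE reporting or vanish from the safety data. The documents do not support that. Section 9.1.4 still makes an event serious on the general criteria, including medical judgement. Section 9.1.5 makes clinically significant laboratory values AEs. Section 9.2.3 asks for a report when it is uncertain that disease is the only cause, and the sentence after the exemption requires 24-hour notice to the sponsor, although it is unclear whether that covers exempted cases. Section 9.5 has the Medical Monitor review AEs as they are reported. This objection stands: only the automatic trigger is at issue.

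**What the protocol calls severe injury.** A reader might also take raised bilirubin or jaundice alone as the stated indicator. Section 9.2.3 gives that status to the combination with ALT/AST above 3 × ULN, with cholestasis and other causes excluded. In subjects with liver metastases, other causes are plausible.

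**Conclusion.** The point holds in a limited form. As written, the exemption is either empty or removes the automatic 24-hour liver SAE trigger from a combined enzyme-bilirubin or enzyme-jaundice event in the 3–5 × ULN band. No reading tried gives it a useful effect. Outside Gilbert Syndrome, the bilirubin elevation in such an event is new since entry.

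It would go too far to conclude that serious liver events will be missed, or that an event certainly counts toward closing an arm while going unreported. The first ignores the remaining reporting routes. The second requires the general list in 9.4 to apply to subjects with liver metastasis, which the document leaves open.

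The number affected is unknown: about 1 to 5 exempt subjects, and probably less than one event, under prevalences and an event rate that are assumptions. The drafting defect does not depend on those figures. It merits correction because it concerns the drug's known liver signal and the correction is small.

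**What to change.** Amend the exemption in Section 9.2.3 so that it covers baseline-type ALT/AST values on their own and does not cancel the trigger when a bilirubin elevation or jaundice is new since baseline. The same amendment should say what treatment-emergent means for a subject whose baseline ALT/AST already exceeds 3 × ULN; otherwise the strict reading would still drop the event through the trigger itself.

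Reconcile 9.2.3 with 9.4 for subjects with liver metastasis: state whether the separate line in 9.4 replaces or adds to the general list, and how an event counted toward halting relates to SAE reporting. The thresholds and any dosing action stay with the sponsor.

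The cost is a sentence or two in an amendment and a few extra SAE reports that prove to be disease progression.
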